3.3.3 Pre-clinical experience with the MVA.tHIVcons4 vaccine

MVA.tHIVcons4 was demonstrated to be safe, non-toxic and immunogenic in over 1,000 BALB/c, C57BL and CD1-SWISS mice during routine experimental immunisations. A formal GLP-compliant acute toxicity study with MVA.tHIVcons4 was deemed not necessary based on the vast cumulative safety data on recombinant MVAs expressing immunogens derived from other pathogens and other immunogens derived from HIV-1 including the very similar first generation conserved-region vaccine MVA.HIVcons collected by us and, for other rMVAs, by many other groups around the world over the last four decades.

3.3.4 Clinical experience with MVA.tHIVconsV3 and MVA.tHIVconsV4

M&M Clinical Trial (NCT03844386) is the first-in-human clinical trial using MVA.tHIVconsV3 and MVA.tHIVconsV4. This is a double blind, randomized, placebo-controlled, parallel design, study in which 24 HIV-infected participants with durable viral suppression will be randomly assigned to receive vaccination with MVA.tHIVconsV3 (M3), MVA.tHIVconsV4 (M4), M3+M4 combined, or placebo. To date, 5 individuals were enrolled; no SAEs were recorded. A non-remarkable safety profile is expected based on numerous previous and ongoing clinical trials using MVA as a viral vaccine vector.

3.3.5 General investigational plan of the vaccines used in the trial

The clinical assessment of the vaccines used in this trial is aimed towards the evaluation of their safety, immunogenicity and efficacy as a part of a multicomponent experimental vaccination regimen developed for prevention and treatment of HIV-1 infection. The full vaccination regimen will encompass priming with non-replicating recombinant simian (chimpanzee) adenoviruses ChAdOx1.tHIVconsV1 + ChAdOx1.HIVconsV62 and boosting with MVA.tHIVconsV3 + MVA.tHIVconsV4. Env component(s) might be added in the future for induction of broadly neutralising antibodies.

For prophylaxis in HIV-1-negative subjects, trial HIV-CORE 0052 will be the first-in-man study in UK healthy adult volunteers. Data derived from HIV-CORE 0052 will provide the ground to design similar studies in different populations. A multi-centre phase 1 trial (HIV-CORE 006) is under preparation with the aim of establishing safety and immunogenicity of the second generation tHIVconsVX vaccines in the ultimate target populations in Kenya, Uganda and Zambia. Other trials in Italy, the US and South Africa will test the safety, immunogenicity and efficacy of similar multicomponent regimens in HIV-1-positive subjects receiving antiretroviral treatment.

3.4 Conducting the trial in the context of the COVID-19 pandemic

To minimise potential risk, clinical activity will be conducted in line with the latest Public Health England (PHE) advice. Local SOPs for the use of appropriate personal protective equipment (PPE) and social distancing will be followed by clinical staff.

Volunteers will receive a generic COVID-19 restrictions information sheet detailing the arrangements that are taking place to allow the trial to continue safely.

They will agree to adhere to PHE advice regarding symptoms and isolation, social distancing and COVID-19 testing (if necessary) while participating in the trial. COVID-19 testing during the trial will be applicable as per PHE guidance and according to symptoms or contacts.

During the COVID-19 pandemic, when government advice prevents non-essential study visits and to limit the risk of unnecessary exposure to COVID-19 enrolment to this trial may be paused, with no screening or vaccination/enrolment visits conducted.

For participants enrolled prior to such governmental advice or between periods of such advice, all scheduled visits may be conducted remotely (via telephone) and the participant will only be asked to attend the clinic if there are any safety concerns. Safety and immunology bloods will be taken at the earliest convenience in an unscheduled visit at discretion of the investigator.

If a volunteer is self-isolating at the time of a scheduled follow-up appointment, they will be assessed via telephone and the appointment will be re-scheduled using the time windows if possible. If this is not possible, all relevant data that can be collected by phone will be recorded in the corresponding eCRF. Safety and immunology bloods will be taken at the earliest convenience in an unscheduled visit at discretion of the investigator.

During the COVID-19 epidemic in the UK, volunteers and their household members will be advised on whether they require to self-isolate according to PHE guidance on vaccinations. No self-isolation is required when fever is an expected vaccination reaction, unless COVID-19 is suspected (e.g. if other symptoms associated with COVID-19 co-exist). Fever which usually resolves within 48 hours is a systemic expected adverse reaction from vaccination with ChAdOx1.tHIVcons1, MVA.tHIVcons3 and MVA.tHIVcons4. If the volunteer is persistently febrile, has other COVID-19 symptoms, or the clinical investigator considers it necessary, the volunteer will be advised to follow PHE guidance on self-isolation and testing.

4. OBJECTIVES AND OUTCOME MEASURES

The purpose of this trial is to determine whether the vaccination regimen is safe, tolerable and immunogenic. The vaccine immunogens tHIVconsVX were designed for maximum match with group M global HIV-1 isolates. This study will test the specificity, magnitude and functionality of T-cell responses after a regimen of one dose of ChAdOx1.tHIVconsV1 prime followed by MVA.tHIVconsV3 and MVA.tHIVconsV4 as a boost.

Objectives	Endpoints/Outcome Measures	Timepoint(s) of evaluation of this outcome measure (if applicable)
Primary Objectives 
 To evaluate the safety and tolerability of ChAdOx1.tHIVconsV1 given alone and in a prime boost vaccine regimen followed by MVA.tHIVconsV3 and MVA.tHIVconsV4 	
 Proportion of volunteers who experience local and systemic reactogenicity events Proportion of volunteers with Grade 3 or 4 unsolicited AEs Proportion of volunteers with vaccine related SAEs 	
 Within 7 days post vaccination Through 28 days post final vaccination Throughout the study period
Secondary Objectives To determine: 
 the proportion of vaccine recipients who develop tHIVconsVX specific T-cell responses induced by the ChAdOx1.tHIVconsV1 followed by MVA.tHIVconsV3 & 4 vaccines To assess: 
 the tHIVconsVX-specific T-cell responses for their frequency, breadth and duration in vaccine responders 	
 Proportion of vaccine recipients developing HIV-1 specific T-cell responses Frequency, breadth and duration of the tHIVconsVX-specific T-cell responses to conserved epitopes measured in the IFN-γ ELISpot assay in each vaccine recipient 	
 At 1 and 20 weeks post final vaccination At 1 and 20 weeks post final vaccination

Objectives	Endpoints/Outcome Measures	Timepoint(s) of evaluation of this outcome measure (if applicable)

 Ability of the tHIVconsvX-specific T-cell responses to inhibit replication in vitro of viruses of four major HIV-1 clades A, B, C and D 	
 Breadth of inhibition of HIV-1 viruses 	
 At 1 and 20 weeks post final vaccination
Exploratory Objectives 
 To assess the plurifunctionality of the tHIVconsvX-specific T-cells in the vaccine responders To characterise the gut microbiome composition and richness 	
 Proportions of mono-, bi- and tri-functional tHIVconsvX specific T-cells in the vaccine recipients Shotgun sequencing and metabolomics analyses 	
 At 1 and 20 weeks post final vaccination Before vaccination, at 1 and 20 weeks post final vaccination

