1. SYNOPSIS

Title	A phase 1 dose escalation open label trial to assess safety and immunogenicity of candidate ChAdOx1- and MVA-vectored conserved mosaic HIV-1 vaccines given sequentially to healthy HIV-1/2-negative adult volunteers in Oxford, UK																
Trial Identifier	HIV-CORE 0052																
Trial Centres	Centre for Clinical Vaccinology & Tropical Medicine, University of Oxford, Churchill Hospital, [name]																
Clinical Phase	1																
Design	Open label																
Population	HIV-1/2-negative, low-risk males and females 18-65 years of age																
Study design	
  
 Group	N	Wk 0	Wk 4	
   
 1	3	C1 (low dose)	-	
 
 2	10	C1 (high dose)	M3M4	
 
 Total	13			
  
 
C1; ChAdOx1.tHIVconsV1 M3; MVA.tHIVconsV3 M4; MVA.tHIVconsV4
	Group	N	Wk 0	Wk 4	1	3	C1 (low dose)	-	2	10	C1 (high dose)	M3M4	Total	13		
Group	N	Wk 0	Wk 4														
1	3	C1 (low dose)	-														
2	10	C1 (high dose)	M3M4														
Total	13																
Visit Schedule	GROUP 1 Seven visits over 4 months; screening, D0 (C1 low-dose vaccination) , D1, D7, D14 (phone call only), D28, D112.																

GROUP 2 Twelve visits over 5 months; screening, **D0 (C1 vaccination)**, D1, D7, D14 (phone call only), **D28, (M3M4 vaccination)**, D29, D35, D42, D56, D84, D140

Planned Trial Period Q2 2021 – Q2 2022

Objectives **PRIMARY**

Safety

- To evaluate the safety and tolerability of ChAdOx1.tHIVconsV1 given alone and in a prime boost vaccine regimen followed by MVA.tHIVconsV3 & 4 in HIV-1/2-negative healthy adults.

SECONDARY

- To determine the proportion of vaccine recipients who developed tHIVconsVX-specific T-cell responses induced by the ChAdOx1.tHIVconsV1 followed by MVA.tHIVconsV3 & 4 vaccines.
- To assess the tHIVconsVX-specific T-cell responses for their frequency, breadth and duration in vaccine responders.
- To assess ability of the tHIVconsVX-specific T-cell responses to inhibit replication *in vitro* of viruses of four major HIV-1 clades A, B, C and D.

EXPLORATORY

- To assess the plurifunctionality of the tHIVconsVX-specific T-cells in the vaccine responders.
- To characterise the gut microbiome composition and richness.

Endpoints**PRIMARY*****Safety***

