5.4 Duration of study

The total duration of the study will be 4 months and 5 months from the day of enrolment, for group 1 and group 2, respectively.

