5.6 Potential risks for volunteers

The potential risks are those associated with phlebotomy and vaccination.

- ***Venepuncture and intravenous cannulation***

The total volume of blood drawn per visit and over the four or five-month study period (less than 100ml for Group 1 participants or less than 600ml for Group 2 participants) is not expected to compromise volunteers' health. This is less than the volume allowed for both male and female blood donors over a similar period, therefore we do not anticipate AEs as a consequence of blood sampling. We will monitor for anaemia at regular intervals, as indicated in the Schedule of Procedures and participants will be asked to refrain from blood donation for the duration of their involvement in the trial.

Mild tenderness, bruising at the site of needle insertion, light-headedness, or rarely, syncope, may result from venepuncture. Study participants will be seated or reclining in order to minimise the risk of the latter.

- ***Allergic reactions***

Allergic reactions from mild to severe may occur in response to any constituent of a medicinal product's preparation. Anaphylaxis is extremely rare (less than 1 in 1,000 people) but can occur in response to any vaccine or medication. Advanced Life Support trained physicians, equipment and drugs are immediately available for the management of any serious adverse reactions (SAR).

- ***Vaccination***

- Local reaction from IM vaccination***

Typical local reactions as a result of IM injections are temporary pain, redness and swelling at the site of the injection.

- Systemic reactions***

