7.1 Schedule of Attendance

All volunteers will have the schedule of clinic attendances and procedures as indicated in the schedules of attendance (Table 2). The total volume of blood to be taken at each visit will vary and can be up to approximately 130 ml. Additional visits or procedures may be performed at the discretion of the investigators, e.g., further medical history and physical examination, blood tests in event of laboratory abnormalities leading to AE, or urine microscopy in the event of positive urinalysis.

2. Schedule of Procedure

2a. Schedule of Procedures of group 1

Visit number	Screen	1	2	3	4	5	6
Study week	Screen	0	1	1	2	4	16
Study day	-42	0	1	7	14¹	28	112²
Visit windows (days)	(≤ -42)	0	-	±3	±3	±3	±7
Informed consent	X						
Confirm eligibility	X	X					
VACCINATION							
ChAdOx1-tHIVconsV1 low dose			X				
COUNSELLING							
HIV Risk Reduction Counselling	X	X					X
HIV Test Counselling	X	X					X
CLINICAL ASSESSMENTS							
HIV-1 Risk Assessment	X						
Comprehensive Medical History	X						
Interim Medical History		X	X	X	X	X	X
General Physical Exam	X	X					
Symptom Directed Physical Exam			X	X		X	X
Weight	X						
Height	X						
Vital signs	X	X ³	X	X		X	X
Cervical & Axillary lymph nodes		X	X	X			
Adverse Events		X	X	X	X	X	X
Serious Adverse Events		X	X	X	X	X	X
Concomitant Medications	X	X	X	X	X	X	X
Local and Systemic Reactogenicity Assessment ¹		X ⁴		X			
LABORATORY PROCEDURES							
HBsAg, HCV Antibodies (5 ml)	X						X
Syphilis serology	X						X
HIV-Ab (5 ml- when HBsAG and HCV Ab are required, no additional blood for HIV-Ab is needed)	X	X					X
HIV-RNA (10 ml)							X
Urinalysis	X						
Routine Haematology (2 ml)	X	X	X	X		X	X
Coagulation screen and fibrinogen (3 ml)	X	X					X
Biochemistry (4 ml)	X	X		X		X	
Pregnancy Test (if applicable)	X	X					X
Blood volume per visit (ml)	21	13	2	6		9	17
Cumulative blood volume (ml)		34	36	42		51	68

¹ Visit D14 will be conducted by phone; participants might need to attend the clinic at discretion of the investigator. If participants attend the clinic, the visit will be recorded as unscheduled visit.

² Early Termination (ET): Procedures to be performed at ET are the same as the week 16 visit procedures.

³ Collect at baseline and at 30 (±5 min) min post vaccination; first participant in each group will have additional observation at 60 min (±5 min)

⁴ Reactogenicity will be collected from Day 0 to Day 7 after each vaccination.

Table 2b. Schedule of procedures of Group 2

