Visit number	Screen	1	2	3	4	5	6	7	8	9	10	11
Study Week	Screen	0	1	1	2	4	4	5	6	8	9	20²
Study day	-42	0	1	7	14¹	28	29	35	42	56	84	140
Visit windows (days)	(≤ -42)	0	0	±3	±3	±3	0	±3	±3	±3	±7	±7
Informed consent	X											
Confirm eligibility	X	X										
VACCINATIONS												
ChAdOx1.tHIVconsV1 high dose		X										
MVA.tHIVconsV3 and MVA.tHIVconsV4							X					
COUSSELLING												
HIV Test Counselling	X	X					X					X
CLINICAL ASSESSMENTS												
HIV-1 Risk Assessment	X											
Comprehensive Medical History	X											
Interim Medical History		X	X	X	X	X	X	X	X	X	X	X
General Physical Exam	X	X				X						
Symptom Directed Physical Exam			X	X			X	X	X	X	X	X
Weight	X											
Height	X											
Vital signs	X	X ³	X	X		X ³	X	X	X	X	X	X
Cervical & Axillary lymph nodes		X	X	X		X	X	X				
Adverse Events		X	X	X	X	X	X	X	X	X	X	
Serious Adverse Events		X	X	X	X	X	X	X	X	X	X	X
Concomitant Medications	X	X	X	X	X	X	X	X	X	X		
Local and Systemic Reactogenicity Assessment ¹		X ⁴	X	X		X ⁴	X	X				
LABORATORY PROCEDURES												
HBsAg, HCV Ab (5 ml)	X											X
Syphilis serology	X											X
HIV-Ab (5 ml- when HBsAG and HCV Ab are required, no additional blood for HIV-Ab is needed)	X	X				X						X
HIV-RNA (10 ml)												X
Urinalysis	X											
Routine Haematology (2 ml)	X	X	X	X		X	X	X	X			X
Coagulation screen and fibrinogen(3 ml)	X	X				X				X		
Biochemistry (4 ml)	X	X		X		X		X	X			
Pregnancy Test (if applicable)	X	X				X						X
Faecal samples		X ⁵						X				X
IMMUNOLOGY												
HLA Typing (4 ml)		X										
Fresh ELISpots (20 ml)		X						X				X
PBMC, serum and plasma storage (frozen ELISpot, VIA, ICS, memory) (100 ml)		X						X	X			X
Epitope Mapping (20 ml)										X	X	
Innate response (2.5 ml)		2.5	2.5	2.5		2.5	2.5	2.5			2.5	2.5
Blood volume per visit (ml)	14	140.5	4.5	8.5	-	16.5	4.5	128.5	100	20	22.5	139.5
Cumulative blood volume (ml)	14	154.5	159	167.5	167.5	184	188.5	317	417	437	459.5	599

¹ Visit D14 will be conducted by phone; participants might need to attend the clinic at discretion of the investigator. If participants attend the clinic, the visit will be recorded as unscheduled visit.

² Early Termination (ET): Procedures to be performed at ET are the same as the week 20 visit procedures.

³ Collect at baseline and at 30 (± 5 min) min post vaccination; first participant in each group will have additional observation at 60 min (± 5 min)

⁴ Reactogenicity will be collected from Day 0 to Day 7 after each vaccination.

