9.4 Reporting procedures for all Adverse Events (see local SOP for AE reporting)

All local and systemic AEs occurring in the 28 days following each vaccination observed by the Investigator or reported by the volunteer, whether or not attributed to study medication, will be

recorded. Recording and reporting of all AEs will take place as detailed in SOP VC027 Adverse Event Data Collection and Analysis. All AEs that result in a volunteer's withdrawal from the study will be followed up until a satisfactory resolution occurs, or until a non-study related causality is assigned (if the volunteer consents to this). SAEs will be collected throughout the entire trial period (D140).

9.4.1 *Reporting procedures for Serious AEs (see local SOP for Safety Reporting)*

In order to comply with current regulations on SAE reporting to regulatory authorities, the event will be documented accurately and notification deadlines respected. SAEs will be reported on the SAE forms to members of the study team immediately when the Investigators become aware of their occurrence, as described in SOP OVC005 Safety Reporting for CTIMPs. Copies of all reports will be forwarded for review to the CI (as the Sponsor's representative) within 24 hours of the Investigator being aware of the suspected SAE. The local safety monitor (LSM) will be notified of SAEs that are deemed possibly, probably or definitely related to study interventions; the LSM will be notified immediately (within 24 hours) of the Investigators' being aware of their occurrence. SAEs will not normally be reported immediately to the ethical committee(s) unless there is a clinically important increase in occurrence rate, an unexpected outcome, or a new event that is likely to affect safety of trial volunteers, at the discretion of the CI, following the advice of the LSM. In addition to the expedited reporting above, all SAEs will be reported in the annual Development Safety Update Report (DSUR) report. Hospitalisations for elective procedures that are planned prior to enrolment into the study will not be reported as SAEs.

9.4.2 *Reporting Procedures for SUSARS*

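### Section 4 dates the late immunogenicity read-out 20 weeks after the last vaccination, but the last Group 2 sample (D140) comes 16 weeks after the D28 boost

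*Combined protocol and SAP*

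**What the plan says.** Section 4 evaluates three secondary endpoints (proportion of responders; frequency, breadth and duration of ELISpot responses; breadth of virus inhibition) "At 1 and 20 weeks post final vaccination". Of the two exploratory endpoints, plurifunctionality has the same timing and the microbiome endpoint reads "Before vaccination, at 1 and 20 weeks post final vaccination".

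The operational sections describe a different late time point:

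- The synopsis gives Group 2 its MVA boost at D28 and then lists visits at "D29, D35, D42, D56, D84, D140". Nothing follows D140.
- Table 2b (Section 7.1) heads the D140 column as study week 20, and its footnote on early termination says "Procedures to be performed at ET are the same as the week 20 visit procedures".
- Section 5.4 states "The total duration of the study will be 4 months and 5 months from the day of enrolment" for Groups 1 and 2 respectively.
- Section 9.4 gives D140 as the end of the trial period for collecting serious adverse events.
- Section 7.3 restricts the research immunology and the faecal samples to Group 2.

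**The concern.** Section 4 names one anchor, the final vaccination, for both of its time points. The early one fits that anchor and the late one does not. The number 20 matches the study-week label of the D140 visit, which counts from enrolment, so two clocks appear to have been mixed in one phrase.

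This matters because duration of response is a named secondary endpoint. The synopsis endpoint list and Section 10 give no immunogenicity time points, so Section 4 alone says when these endpoints are evaluated. Read literally, the late evaluation has no scheduled sample. If the D140 results are reported under the Section 4 label, the vaccine response will appear to have been followed for longer than it was. Section 3.3.5 says the data will inform the design of similar studies, so the error could carry forward.

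**Working it through.** **Inputs**

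- Final vaccination, Group 2: D28 (synopsis), window ±3 days (Table 2b).
- Last visit, Group 2: D140 (synopsis, Table 2b, Section 9.4), window ±7 days (Table 2b).
- Fresh ELISpot and faecal samples: D0, D35 and D140. PBMC storage: D0, D35, D42 and D140 (Table 2b).
- Last visit, Group 1: D112, ±7 days, after a single vaccination at D0 (Table 2a, whose footnote reads "Procedures to be performed at ET are the same as the week 16 visit procedures").

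**1. Where the stated 20 weeks comes from.** Weeks elapsed = (visit day − anchor day) / 7.

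- From enrolment: (140 − 0) / 7 = 20.0 weeks.
- From the final vaccination: (140 − 28) / 7 = 112 / 7 = 16.0 weeks.

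The stated figure is reproduced only from enrolment.

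**2. The early time point.** (35 − 28) / 7 = 1.0 week from the final vaccination, so this part of the phrase is right at nominal dates.

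**3. Where a true 20-week sample would fall.** 28 + 20 × 7 = D168, and 168 − 140 = 28 days after the last visit.

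**4. Whether the windows can close the gap.** The protocol does not say whether the D140 window counts from enrolment or from the actual boost date, so both readings are shown.

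| Reading | Shortest | Longest | Short of 20 weeks by |
|---|---|---|---|
| Both windows counted from D0 | (133 − 31) / 7 = 14.6 weeks | (147 − 25) / 7 = 17.4 weeks | (25 + 140) − 147 = 18 days to (31 + 140) − 133 = 38 days |
| D140 counted from the actual boost | (112 − 7) / 7 = 15.0 weeks | (112 + 7) / 7 = 17.0 weeks | 140 − 119 = 21 days to 140 − 105 = 35 days |

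Neither reading reaches 20 weeks.

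**5. Other anchors.**

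- In the extracted Table 2b the MVA mark sits under D29, possibly a conversion shift. That would give (140 − 29) / 7 = 15.9 weeks.
- Group 1 has no immunology, and its last visit is 112 / 7 = 16.0 weeks after its only vaccination (15.0 to 17.0 with the window).

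**6. Consistency with study duration.** At 30.4375 days per month, D140 is 4.6 months and D168 is 5.5 months. Only D140 fits within the 5 months of Section 5.4.

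**7. Whether the late samples are planned.** D140 blood in Table 2b: 5 + 10 + 2 + 20 + 100 + 2.5 = 139.5 ml, as printed. This includes the 20 ml fresh ELISpot and 100 ml PBMC draws.

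**The case against.** The strongest reply is that this is a labelling slip. The synopsis, Section 5.4, Table 2b and Section 9.4 agree with one another, no visit or sample is missing, and the endpoints concerned are secondary or exploratory in a descriptive, open-label trial of 13 people. The harm arises only if the report copies the Section 4 label instead of the visit day. Section 10 also refers to an agreed statistical analysis plan, and Section 7.3 to a laboratory plan. Neither is reproduced in the available text, and either might use the right label.

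Much of this stands: the effect is confined to how results are dated, and the harm is conditional. It does not remove the error. Within these documents no other passage dates these endpoints, and an analyst who follows the definition would either look for a sample that is not scheduled or misstate the follow-up.

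A second objection also stands in part. The 14.6 to 17.4 week range assumes that both windows run from D0. Table 2b gives D29 no window although D28 has ±3 days, and Section 7.3 requires haematology one day after each vaccination. That visit, at least, must therefore follow the actual boost. If D140 does so too, the range is 15.0 to 17.0 weeks. The same uncertainty applies to the early sample: D35 falls between 32 − 31 = 1 and 38 − 25 = 13 days after the boost if both windows run from D0, or 4 to 10 days if it follows the actual boost. None of this makes 20 weeks attainable.

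The COVID-19 provisions in Section 3.4 allow blood at unscheduled visits, at the investigator's discretion. That is a contingency and does not amount to a planned 20-week sample.

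**Conclusion.** The point holds. Section 4 and the visit schedule contradict each other on the late time point of five endpoints, three secondary and two exploratory. The plan states 20 weeks after the final vaccination and schedules 16.0 weeks, a difference of 28 days at nominal dates and at least 18 days under the most favourable reading of the windows. Reported as labelled, the follow-up of the response would be overstated by 4 weeks on a true 16.

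The conclusion rests only on the boost at D28 and the last visit at D140, both stated in the synopsis. It should be corrected before the immunogenicity data are reported.

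**What to change.** Reconcile Section 4 with Table 2b. With the schedule as it stands, change the late time point in all five entries to 16 weeks after the last vaccination (D140, study week 20), and limit conclusions on duration to 16 weeks after the boost. This costs no visit, sample or blood; the price is a durability statement 4 weeks shorter. Giving the study day beside every week label would prevent a recurrence. Table 2b also shows D84 as study week 9, although 84 / 7 = 12. It would help to state whether post-boost windows count from enrolment or from the actual boost.

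If the sponsor meant 20 weeks after the boost, rewording is not enough. The visit would fall at D168, and the synopsis, Section 5.4, Table 2b and the D140 trial end in Section 9.4 would all need amending. If the ELISpot and PBMC samples were added at D168 and not moved there, the printed cumulative volume would rise from 599 to 599 + 20 + 100 = 719 ml, against "less than 600ml for Group 2 participants" in Section 5.6. The printed 599 ml should itself be checked first. As extracted, the table marks haematology (2 ml) and biochemistry (4 ml) at D42 and coagulation (3 ml) at D56, but the visit totals of 100 and 20 ml leave out these 9 ml, which would make the present total 608 ml.
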